10.2.1 Guidance for management of muscle symptoms and CK elevations

If confirmed CK elevation > 5 fold ULN and other causes such as exercise are excluded, lab follow up and management according to the guidance for management of muscle symptoms and CK elevations as described in this section should be followed.

- Lab follow up (central lab analysis preferred) includes:
 - Serum: CK (incl. isoforms), creatinine, urea nitrogen, uric acid and calcium, potassium, phosphate, Prothrombin time (PT), thyroid stimulating hormone (TSH)
 - Urine: urinalysis incl. myoglobin and sediment.
- Throughout the study, subjects should be instructed to promptly report unexplained muscle pain or weakness, particularly if associated with malaise or fever. If this occurs, CK should be measured as soon as possible.
- If CK is found to be elevated $\geq 5 \times ULN$ on routine testing, the subject should be questioned about muscle symptoms and re-tested within 3 days.
- A suitably-experienced physician should be involved in deciding appropriate management for the subject. The physician should be alerted to the occurrence of unexplained muscle symptoms, and any CK values $\geq 5 \times ULN$ and must take immediate action if CK > 10 x ULN.
- For $CK > 10 \times ULN$ (confirmed, 2^{nd} sample required) with or without muscle symptoms, discontinue study drug.
- For $CK > 5 10 \times ULN$ (confirmed, 2^{nd} sample required)
 - If symptomatic and no alternative explanation exists, withhold therapy.
 - If symptomatic, or if symptomatic but alternative explanation exists, follow symptoms and CK level weekly until there is no longer medical concern or symptoms worsen and meet criteria above
- The following questioning and follow-up investigations should be performed:
 - Clarify the nature, duration and intensity of relevant symptoms
 - Clarify and document whether the patient was taking study treatment at the time of the event, or when the last done of study treatment was taken. Document dosing information in source and report if appropriate (e.g., if considered an SAE).

- Review possible predisposing factor, such as: unaccustomed exercise (including decorating, gardening, etc.), heavy alcohol intake, viral illness or severe bacterial infections (consider performing serology), concomitant medications (e.g., anesthetics, cholesterol-lowering agents – niacin, clofibrate, statins, ezetimibe, glucocorticoids, narcotic, chloroquine etc.) and consider diagnosis of other conditions which can cause myopathy (e.g. trauma).
 - \rightarrow Physical examination for muscle tenderness, weakness and rash
 - \rightarrow Measure lab parameters (as described above) within a few days
 - → Arrange to review the participant again in 4 to 10 days, or if symptoms of myopathy appear or worsen, or if the urine becomes very dark
- Myopathy is defined as muscle aches or weakness in association with CK increased to > 10 x ULN. If myopathy occurs or if on clinical grounds, statin-induced myopathy is diagnosed or suspected, statin therapy should be discontinued. Myopathy should always be recorded as an adverse event, and the Bayer representative must be informed.
- If the study treatment is temporarily disrupted, it is suggested that the Bayer representative be consulted before restarting study treatment.
- The Bayer representative should be consulted prior to permanently withdrawing a participant.

10.3 Appendix 3: Adverse events: Definitions and Procedures for Recording, Evaluating, Follow-up, and Reporting

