8.3.4 Clinical Safety Laboratory Tests

• See Section 10.2 for the list of clinical laboratory tests to be performed and the SoA (Section 1.3) for the timing and frequency.

Note: If screening laboratory assessments were done at Visit 1, only CRP, blood count, and urinalysis must be re-assessed at Visit 2.

- The investigator must review the laboratory report, document this review, and record any clinically significant changes occurring during the study as an AE. The laboratory reports must be filed with the source documents.
- Abnormal laboratory findings associated with the underlying disease are not considered clinically significant unless judged by the investigator to be more severe than expected for the participant's condition.
- All laboratory tests with values considered clinically significantly abnormal during participation in the study or within 28 days after the last dose of study intervention should be repeated until the values return to normal or baseline or are no longer considered clinically significant by the investigator or the medical monitor.
 - If clinically significant values do not return to normal/baseline within a period of time judged reasonable by the investigator, the etiology should be identified, and the sponsor notified.
 - All protocol-required laboratory tests, as defined in Section 10.2, must be conducted in accordance with the laboratory manual and the SoA.
 - If laboratory values from non-protocol-specified laboratory tests performed at the institution's local laboratory require a change in participant management or are considered clinically significant by the investigator (e.g., SAE or AE or dose modification), then the results must be recorded.
- Laboratory abnormalities leading to discontinuation of study intervention are listed in Section 7.

8.3.5 **Pregnancy Testing**

The defined time points for pregnancy testing are displayed in the SoA (see Section 1.3).

Zabedosertib was non-genotoxic. In addition, it did not show a phototoxic potential.

In the developmental toxicity studies in mice, effects on fetuses were seen starting at the low dose with a higher incidence of cleft palates at the high dose. No effects were seen in the pilot and pivotal embryofetal development studies in rabbits up to the maximum feasible dose tested.

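### Protocol 10.2.1: as printed, asymptomatic participants with confirmed CK >5–10 × ULN fall outside both rules for that band and lose the weekly CK follow-up

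*Protocol*

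**What the plan says.** Protocol Section 10.2.1 is the guidance for muscle symptoms and CK elevations. Its opening sets no symptom condition: "If confirmed CK elevation > 5 fold ULN and other causes such as exercise are excluded, lab follow up and management" are to follow the section.

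Two ranges of confirmed CK then get specific actions:

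- **Above 10 × ULN:** "with or without muscle symptoms, discontinue study drug".
- **>5–10 × ULN, first sub-bullet:** "If symptomatic and no alternative explanation exists, withhold therapy".
- **>5–10 × ULN, second sub-bullet:** "If symptomatic, or if symptomatic but alternative explanation exists, follow symptoms and CK level weekly". This continues until medical concern has passed or symptoms worsen enough to meet the earlier criteria.

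The section also has general steps that do not depend on symptoms. For CK at or above 5 × ULN on routine testing, "the subject should be questioned about muscle symptoms and re-tested within 3 days". An experienced physician is alerted and helps decide management. Further steps are "Measure lab parameters (as described above) within a few days" and "Arrange to review the participant again in 4 to 10 days, or if symptoms of myopathy appear or worsen".

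Section 8.3.4 adds that clinically significant abnormal values "should be repeated until the values return to normal or baseline", or until they are no longer judged significant. It names no interval.

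**The concern.** The second sub-bullet cannot be what its authors intended. A participant who is symptomatic with an alternative explanation is already symptomatic, so the second half of the condition adds nothing to the first. The line also covers the participants whom the first sub-bullet has just dealt with, and neither line names asymptomatic participants.

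This guidance matters in this trial. Table 2-1 (Section 2.3.1) lists five measures against rhabdomyolysis, prompted by a fatal case with another molecule of the class. Frequent CK testing and this guidance are two of them. An asymptomatic participant has no symptom to prompt an early visit, so follow-up depends on dated tests. What is at stake is the recurring weekly CK test for a participant whose CK is confirmed above 5 × ULN and who is still taking study drug.

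**Working it through.** **Step 1: map each case to the two sub-bullets for confirmed CK >5–10 × ULN.**

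| Case | As printed | With *asymptomatic* as the first condition |
|---|---|---|
| Symptomatic, no alternative explanation | Withhold, and weekly follow-up | Withhold |
| Symptomatic, alternative explanation | Weekly follow-up | Weekly follow-up |
| Asymptomatic | Neither | Weekly follow-up |

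With the one-word change, every case gets exactly one sub-bullet. The stopping condition points the same way. Weekly follow-up ends when symptoms worsen enough to meet the earlier criteria, so the line was written for people who do not yet meet them. A symptomatic participant with no explanation already does. The neighbouring rule above 10 × ULN and the opening sentence both include asymptomatic participants.

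**Step 2: look for a weekly or other recurring CK interval elsewhere.**

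- Section 7.1 requires discontinuation only for confirmed CK above 10 × ULN or clinical signs of rhabdomyolysis.
- Section 7.1.3 (temporary discontinuation) has no CK item.
- Table 2-1 mentions discontinuation for elevated CK but gives no threshold.
- Table 10-1, footnote 2, lists the laboratory follow-up panel without an interval.
- Section 8.3.4 requires repeats without an interval.
- SAP Section 4.5.3 counts participants with CK of 5 to 10 × ULN but sets no monitoring.

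No recurring interval was found.

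**Step 3: time without a protocol-dated CK test.**

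Inputs: visit days and windows from the Schedule of Activities (Section 1.3) are 14 ± 2, 28 ± 2, 56 ± 3 and 84 ± 3. CK is in the safety panel at each of these visits (Table 10-1). The general review falls 4 to 10 days after detection (Section 10.2.1).

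- Day 28 to Day 56: nominal 56 − 28 = 28 days; longest 59 − 26 = 33.
- Day 56 to Day 84: nominal 84 − 56 = 28 days; longest 87 − 53 = 34.
- From review to next scheduled CK, nominal: 28 − 10 = 18 to 28 − 4 = 24 days.
- Longest with windows: 34 − 4 = 30 days. Shortest, with Visit 6 late, Visit 7 early and review on day 10: (81 − 59) − 10 = 12 days.
- Detection at Day 14, nominal: the interval is 28 − 14 = 14 days, which leaves only 14 − 10 = 4 to 14 − 4 = 10 days.

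**Step 4: weekly tests lost.** Weekly tests strictly inside a 28-day interval fall on days 7, 14 and 21 after detection, which is 3 tests. The general review can stand in for at most 1, so 3 − 1 = 2 have no stated date.

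**The case against.** The strongest reply is that asymptomatic participants are far from unattended. Symptom questioning and a re-test within 3 days, the physician alert, the follow-up panel, laboratory tests within a few days and the 4-to-10-day review all apply without symptoms. Section 8.3.4 keeps clinically significant values under repeat testing until they resolve, and Section 10.2 allows extra tests at any time. This stands. A reader might infer that these participants get no instruction, or go up to 30 days without CK testing, and the documents do not support either. The interval is time without a *protocol-dated* test. It becomes time without any test only if the investigator and physician order nothing. What the general steps do not provide is a recurring interval, and Section 8.3.4 depends on the value being judged clinically significant.

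Second, the point turns on one letter, which could have been lost between the sponsor's source file and the public copy. This cannot be excluded, although the prose around the bullet reads cleanly. It is a reason to check the source first.

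Third, a careful site could work out the intent, since asymptomatic is the only case left over. That is probably true, but an operative safety rule should not rely on sites inferring it.

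Fourth, the 30-day figure needs Visit 6 three days early, Visit 7 three days late and review on day 4. That is correct, so 18 to 24 days is the figure to use.

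**Conclusion.** The concern holds as a wording defect in a safety-monitoring rule. As printed, asymptomatic participants with confirmed CK >5–10 × ULN fall outside both sub-bullets and lose the weekly symptom and CK follow-up. For a rise found at Day 28 or Day 56, 18 to 24 days (at most 30) can pass after the review with no dated CK test, and 2 of 3 weekly tests have no stated date.

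These figures assume that the review is counted from detection and that CK is measured at it. The text states neither. If CK is not measured at the review, the undated period starts earlier and is longer. The documents give no rate of CK elevation, so no number of affected participants can be given.

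A reader might also infer that the overlap tells sites to keep dosing a symptomatic participant. It does not: weekly follow-up is compatible with withholding, and the withhold line still applies. The discontinuation rule above 10 × ULN is clear. No endpoint, analysis or sample size is affected. The point deserves correction because the rule belongs to a named risk mitigation and the remedy is nearly free.

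**What to change.** Check the sub-bullet against the source file. If the public copy is faithful, and once the sponsor's medical team confirms the intent, change the first *symptomatic* in the second >5–10 × ULN sub-bullet to *asymptomatic*. Leave the rest of the sentence unchanged, including its stopping condition. A clarification letter or non-substantial amendment should be enough.

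The cost is about 2 extra CK samples per 28-day interval for an affected asymptomatic participant, with no change to the analysis or sample size.

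The same document could carry a separate clerical correction that is not part of this point. Exclusion criterion 24 prints 200/mm³ beside 2.0 × 10⁹/L, where the equivalent is 2000/mm³, as in Section 5.4. The leading unit already makes the limit clear.

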10.3.1 Definition of AE

AE Definition

- An AE is any untoward medical occurrence in a clinical study participant, associated with the use of study intervention, whether or not considered related to the study intervention.
- NOTE: An AE can therefore be any unfavorable and unintended sign (including an abnormal laboratory finding), symptom, or disease (new or exacerbated) associated with the use of study intervention.

Definition of Unsolicited and Solicited AE

- An unsolicited adverse event is an adverse event that was not solicited using a participant diary and that is communicated by a participant who has signed the informed consent. Unsolicited AEs include serious and nonserious AEs.
- Potential unsolicited AEs may be medically attended (i.e., symptoms or illnesses requiring a hospitalization, emergency room visit, or visit to/by a healthcare provider). The participant will be instructed to contact the site as soon as possible to report medically attended event(s), as well as any events that, though not medically attended,

are of participant concern. Detailed information about reported unsolicited AEs will be collected by qualified site personnel and documented in the participant's records.

• Unsolicited AEs that are not medically attended nor perceived as a concern by the participant will be collected during an interview with the participant and by review of available medical records at the next visit.

Solicited AEs are predefined local and systemic events for which the participant is specifically questioned, and which are noted by the participant in their diary.

Events Meeting the AE Definition

- Any abnormal laboratory test results (hematology, clinical chemistry, or urinalysis) or other safety assessments (e.g., ECG, radiological scans, vital signs measurements), including those that worsen from baseline, considered clinically significant in the medical and scientific judgment of the investigator (i.e., not related to progression of underlying disease).
- Exacerbation of a chronic or intermittent pre-existing condition including either an increase in frequency and/or intensity of the condition.
- New conditions detected or diagnosed after study intervention administration even though it may have been present before the start of the study.
- Signs, symptoms, or the clinical sequelae of a suspected intervention-intervention interaction.
- Signs, symptoms, or the clinical sequelae of a suspected overdose of either study intervention or a concomitant medication. Overdose per se will not be reported as an AE/SAE unless it is an intentional overdose taken with possible suicidal/self-harming intent. Such overdoses should be reported regardless of sequelae.
- Sign, symptoms, or the clinical sequelae of suspected medication errors, misuse and abuse of either study intervention or a concomitant medication. Medication errors, misuse and abuse per se will not be reported as an AE/SAE, unless it is resulting in AE/SAE. Such medication errors, misuse and abuse should be reported regardless of sequelae.
- Lack of efficacy or failure of expected pharmacological action per se will not be reported as an AE or SAE. Such instances will be captured in the efficacy assessments. However, the signs, symptoms, and/or clinical sequelae resulting from lack of efficacy will be reported as AE or SAE if they fulfill the definition of an AE or SAE.

Events NOT Meeting the AE Definition

- Any abnormal laboratory findings or other abnormal safety assessments that are associated with the underlying disease, unless judged by the investigator to be more severe than expected for the participant's condition
- The disease/disorder being studied or expected progression, signs, or symptoms of the disease/disorder being studied, unless more severe than expected for the participant's condition
- Medical or surgical procedure (e.g., endoscopy, appendectomy): the condition that leads to the procedure is the AE
- Situations in which an untoward medical occurrence did not occur (social and/or convenience admission to a hospital)

• Anticipated day-to-day fluctuations of pre-existing disease(s) or condition(s) present or detected at the start of the study that do not worsen

10.3.2 Definition of SAE

An SAE is defined as any untoward medical occurrence that, at any dose, meets the one or more of the criteria listed:

a. Results in death

b. Is life threatening

• The term *life threatening* in the definition of *serious* refers to an event in which the participant was at risk of death at the time of the event. It does not refer to an event, which hypothetically might have caused death, if it were more severe.

c. Requires inpatient hospitalization or prolongation of existing hospitalization

- In general, hospitalization signifies that the participant has been admitted (usually involving at least an overnight stay) at the hospital or emergency ward for observation and/or treatment that would not have been appropriate in the physician's office or outpatient setting. Complications that occur during hospitalization are AEs. If a complication prolongs hospitalization or fulfills any other serious criteria, the event is serious. When in doubt as to whether hospitalization occurred or was necessary, the AE should be considered serious.
- Hospitalization for elective treatment of a pre-existing condition that did not worsen from baseline is not considered an AE.

d. Results in persistent or significant disability/incapacity

- The term disability means a substantial disruption of a person's ability to conduct normal life functions.
- This definition is not intended to include experiences of relatively minor medical significance such as uncomplicated headache, nausea, vomiting, diarrhea, influenza, and accidental trauma (e.g., sprained ankle) that may interfere with or prevent everyday life functions but do not constitute a substantial disruption.

e. Is a congenital anomaly/birth defect

f. Other situations:

- Medical or scientific judgment should be exercised by the investigator in deciding whether SAE reporting is appropriate in other situations such as significant medical events that that may not be immediately life-threatening or result in death or hospitalization but may jeopardize the participant or may require medical or surgical intervention to prevent one of the other outcomes listed in the above definition. These events should usually be considered serious.
 - Examples of such events include invasive or malignant cancers, intensive treatment in an emergency room or at home for allergic bronchospasm, blood dyscrasias, convulsions, or development of intervention dependency or intervention abuse.

10.3.3 Recording and follow-up of AE and/or SAE

AE and SAE Recording

- When an AE/SAE occurs, it is the responsibility of the investigator to review all documentation (e.g., hospital progress notes, laboratory reports, and diagnostics reports) related to the event.
- The investigator will then record all relevant AE/SAE information in the CRF.
- It is not acceptable for the investigator to send photocopies of the participant's medical records to the sponsor in lieu of completion of the AE/SAE CRF page.
- There may be instances when copies of medical records for certain cases are requested by the sponsor. In this case, all participant identifiers, with the exception of the participant number, will be redacted on the copies of the medical records before submission to the sponsor.

The investigator will attempt to establish a diagnosis of the event based on signs, symptoms, and/or other clinical information. Whenever possible, the diagnosis (not the individual signs/symptoms) will be documented as the AE/SAE.

Assessment of Intensity

- The investigator will make an assessment of intensity for each AE and SAE reported during the study and assign it to one of the following categories:
 - Mild: A type of adverse event that is usually transient and may require only minimal treatment or therapeutic intervention. The event does not generally interfere with usual activities of daily living.
 - Moderate: A type of adverse event that is usually alleviated with additional specific therapeutic intervention. The event interferes with usual activities of daily living, causing discomfort but poses no significant or permanent risk of harm to the research participant.
 - Severe: A type of adverse event that interrupts usual activities of daily living, or significantly affects clinical status, or may require intensive therapeutic intervention.

Assessment of Causality

- The investigator is obligated to assess the relationship between study intervention and each occurrence of each AE/SAE. The investigator will use clinical judgment to determine the relationship.
- A *reasonable possibility* of a relationship conveys that there are facts, evidence, and/or arguments to suggest a causal relationship, rather than a relationship cannot be ruled out.
- Alternative causes, such as underlying disease(s), concomitant therapy, and other risk factors, as well as the temporal relationship of the event to study intervention administration will be considered and investigated.
- For causality assessment, the investigator will also consult the IB and/or product information, for marketed products.
- The investigator must review and provide an assessment of causality for each AE/SAE and document this in the medical notes There may be situations in which an SAE has occurred and the investigator has minimal information to include in the initial report to

the sponsor. However, it is very important that the investigator always make an assessment of causality for every event before the initial transmission of the SAE data to the sponsor.

- The investigator may change his/her opinion of causality in light of follow-up information and send an SAE follow-up report with the updated causality assessment.
- The causality assessment is one of the criteria used when determining regulatory reporting requirements.

Follow-up of AEs and SAEs

- The investigator is obligated to perform or arrange for the conduct of supplemental measurements and/or evaluations as medically indicated or as requested by the sponsor to elucidate the nature and/or causality of the AE or SAE as fully as possible. This may include additional laboratory tests or investigations, histopathological examinations, or consultation with other health care professionals.
- If a participant dies during participation in the study or during a recognized follow-up period, the investigator will provide the sponsor with a copy of any postmortem findings including histopathology.
- New or updated information will be recorded in the originally submitted documents.
- The investigator will submit any updated SAE data to the sponsor within 24 hours of receipt of the information.

